Hypothesis: Patients with DMII have significant amylin deposition in the peripheral vasa nervorum and on RBCs that correlates with severity of clinical peripheral polyneuropathy and reduction of peripheral nerve conduction velocities (NCVs); these amylin measures thereby become surrogates of microvascular disease and may serve as metrics of disease severity. Aim: Obtain serum HbA1c, skin punch biopsy, RBCs, NCVs and clinical sensory examination from forty consenting adults previously diagnosed with DMII. Skin biopsy from volar forearm and red blood cell samples will be processed for amylin deposition. This pilot study will provide preliminary data to fuel a larger, potentially multi-center, clinical trial investigating the utility of peripheral amylin or RBC amylin as a quantitative biomarker of microvascular disease that would include monitoring the effect of potential therapies. Measuring serum HbA1c will allow for possible correlation to chronic extracellular glucose concentration. Based on our preliminary data from a rat model of type-2 diabetes that expresses human amylin in the pancreas, we anticipate an increased amylin deposition in the skin blood vessels with the progression of type-2 diabetes as measured by sensory examination and NCVs. The ability to easily identify and target a potential driver of microvascular disease may help prevent the devastating effects of the vascular complications of DMII, including cardiovascular disease, retinopathy, nephropathy and dementia.

Study Design: Describe the study design (e.g., single/double blind, parallel, crossover, etc.). Indicate whether or not the subjects will receive placebo medication at some point in the research procedures. Also, indicate whether or not the subjects will be randomized in this study. You may reference sponsor's protocol pages and attach as an appendix in the E-IRB "Additional Information" section. (Including the study design table from a sponsor's protocol is helpful to IRB members.)

Community-Based Participatory Research: If you are conducting [community-based participatory research \(CBPR\)](#), describe strategies for involvement of community members in the design and implementation of the study, and dissemination of results from the study.

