weight (to calculate body mass index [BMI]), family history of neuropathy, and results of blood tests if obtained within the previous 6 months to include comprehensive metabolic profile, complete blood count, lipid profile, vitamin B12, and thyroid stimulating hormone to help exclude other common causes of peripheral neuropathy. Participants will then undergo a skin biopsy taken from the volar forearm using a standardized kit and vibratory sensation will be measured over the tip of the 2nd digit (index finger) quantified using a Rydel-Seiffer 128 Hz tuning fork), and venipuncture for blood samples utilizing the UK Healthcare Clinical Laboratories. Blood samples will be collected for measure of RBC amylin (performed in [name] laboratory) and HbA1c (UK Healthcare Clinical Laboratories), as well as those measures not performed in the previous 6 months to include metabolic profile, complete blood count, vitamin B12, and thyroid stimulating hormone. Skin biopsies will be collected and stored in formalin. The formalin-fixed skin biopsy will be paraffin embedded and sectioned for staining with an anti-amylin antibody as previously described (15). RBCs will be harvested from collected samples. Cells will be lysed, protein concentration will be determined, and amylin will be detected by immunofluorescence using enzyme-linked immunosorbent assay (ELISA) (14, 15). The positive control for the amylin antibody is the pancreatic tissue from a patient with type-2 diabetes. Negative controls for the amylin antibody are pancreatic and liver tissues from amylin knockout (AKO) rats. Immunohistochemical staining and co-staining of the skin tissue with anti-amylin and anti-collagen IV antibodies will be performed to assess the level of amylin deposition in the skin sample and the localization of amylin deposition with respect to the blood vessel wall. To assess the density of the blood vessels that have amylin deposition, the tissue will be co-stained with anti-amylin and anti-collagen IV antibodies; co-localization will be analyzed using immunoconfocal microscopy (14). One week after NCV, biopsy, and venipuncture, participants will be scheduled for Pain Tests (see below) conducted at the Straus Behavioral Science Building, UKMC. Statistical analysis: The two measures of amylin will be compared using the Bland Altman procedure to determine how well the less invasive measure obtained from RBCs agrees with the more invasive punch biopsy measure. Then each amylin measure will be correlated with the Hba1c and NCV/sensory examination measures to determine how well these levels correlate with a measure of glucose control and with severity of neurologic disease. Correlations will be based on Pearson's correlation coefficient. With a sample size of 40 patients this will have 80% power to detect a correlation at least as large as 0.414 at the 0.05 level of significance. The statistical design has been discussed with [name], consulting statistician for UK COM.

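### Bland-Altman is planned between a red-cell ELISA level and a skin immunostaining readout with no stated common scale, so it cannot show how well RBC amylin agrees with the biopsy measure

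*Protocol*

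**What the plan says.** The statistical analysis text sits at the end of the Study Design section of the protocol. Its first step is: "The two measures of amylin will be compared using the Bland Altman procedure to determine how well the less invasive measure obtained from RBCs". The rest of that sentence sets the goal, namely to see how well this value "agrees with the more invasive punch biopsy measure". Both the method and the question, agreement, are therefore fixed in the protocol.

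The same section describes how the two measures are obtained.

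- **Red cells:** "Cells will be lysed, protein concentration will be determined, and amylin will be detected by immunofluorescence using enzyme-linked immunosorbent assay".
- **Skin:** sections of the formalin-fixed biopsy are stained and co-stained "to assess the level of amylin deposition in the skin sample and the localization of amylin deposition with respect to the blood vessel wall". Confocal co-localization is then added: "To assess the density of the blood vessels that have amylin deposition".

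The second step is: "Then each amylin measure will be correlated with the Hba1c and NCV/sensory examination measures". These are Pearson correlations. The pair RBC amylin and skin amylin is not among them.

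The Objectives section says the pilot is to feed a larger trial of "the utility of peripheral amylin or RBC amylin as a quantitative biomarker of microvascular disease".

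**The concern.** Limits of agreement are built from the difference between two paired readings. That difference has a meaning only if both readings estimate the same quantity in the same unit. The protocol describes readouts that differ in assay (ELISA against immunostaining), in compartment (lysed red cells against vessels in fixed skin) and in kind (an amount against a staining level, a position or a count of vessels). It gives no unit, common scale or conversion, and it does not say which skin readout is the biopsy measure.

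What is at stake is the only planned analysis that relates the less invasive measure to the more invasive one. On the raw scale, the plot could look good or poor for reasons of unit alone. How the two measures relate would be useful preliminary data for the larger trial, and the plan as written does not deliver it.

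**Working it through.** **The plan's own figure.** The only computed figure in this part of the protocol is 80% power for a correlation of 0.414 with 40 patients at the 0.05 level. It reproduces with a noncentral t on 38 degrees of freedom, two-sided (power 0.8004). A Fisher z calculation gives 0.764 and a bivariate-normal simulation 0.775. The figure concerns the correlations and does not bear on Bland-Altman, for which the protocol gives no figure.

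**Inputs.** The protocol gives no mean, SD or unit for either amylin measure, so the following are assumptions for illustration: RBC amylin mean 10, SD 4; skin readout mean 30, SD 15. The factor k rescales the RBC unit (k = 1, 3, 1000). The correlation r runs from 0 to 1.

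**Raw scale.** Bias = 10k - 30. SD of the difference = sqrt((4k)² + 15² - 2·r·4k·15). Limits = bias ± 1.96 × that SD.

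| RBC unit | Bias | Half-width, r = 0 | r = 0.8 | r = 1 |
|---|---|---|---|---|
| k = 1 | -20 | 30.4 | 23.6 | 21.6 |
| k = 3 | 0 | 37.7 | 17.6 | 5.9 |
| k = 1000 | +9970 | 7840 | 7816 | 7811 |

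Example, k = 1 and r = 0.8: sqrt(16 + 225 - 96) = 12.04, and 1.96 × 12.04 = 23.6. For k = 3 and r = 0.8: sqrt(144 + 225 - 288) = 9.00, giving 17.6.

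Three things follow.

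- The bias depends only on the unit and on no property of the patients' paired values.
- With k = 1000 the whole range of r moves the half-width from 7840 to 7811, or 29/7840 = 0.4%.
- A perfect linear relation in one RBC unit (k = 1, r = 1: ±21.6) looks worse than an imperfect one in another (k = 3, r = 0.8: ±17.6).

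A second set of assumed values gives the same picture. With RBC mean 10, SD 2, and the skin readout an exact linear function of it (r = 1), the bias is 5.0 if skin has mean 5 and SD 1.5, -20.0 if mean 30 and SD 8, and +9.7 if that last readout is written as a fraction (mean 0.30, SD 0.08).

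**Log scale.** The coefficients of variation are 4/10 = 0.4 and 15/30 = 0.5. With sigma = sqrt(ln(1 + CV²)), the log SDs are 0.385 and 0.472. The geometric mean ratio is (10k/sqrt(1.16)) / (30/sqrt(1.25)) = 0.35, 1.04 and 346 for k = 1, 3 and 1000. The limits are that ratio times or divided by exp(1.96 × SD of the log difference), with r taken as the correlation of the logs. The SD is 0.610 at r = 0 (factor 3.30) and 0.284 at r = 0.8 (factor 1.74), for all three units. The width no longer depends on the unit; the bias still does.

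**z-scores.** Bias is 0 by construction. Limits = ±1.96 × sqrt(2(1 - r)) = ±2.77, 1.75 and 1.24 for r = 0, 0.6 and 0.8. These contain nothing beyond r.

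**What 40 patients can support instead.**

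- *Confidence interval for r:* tanh(atanh(r) ± 1.96/sqrt(37)). For r = 0.6 it is 0.35 to 0.77; for r = 0.8, 0.65 to 0.89.
- *95% prediction half-width for the skin readout at mean RBC amylin, in SDs of the skin readout:* t(0.975, 38) × sqrt((1 - r²) × 39/38) × sqrt(1 + 1/40), with t = 2.024. This is 2.08 at r = 0, 1.66 at r = 0.6 and 1.25 at r = 0.8.

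**The case against.** The strongest reply has four parts.

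1. **The protocol does not say the analysis will be on the raw scale.** On logs or z-scores the limits do narrow as the association strengthens. That is true, and on those scales the width carries information. It is information about association, however. The log-scale bias is still set by units, the z-score bias is zero whatever the data, and a ratio of two different quantities is not agreement.

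2. **Units, transformation and the choice of skin readout may be in an analysis plan, the cited assay papers or the attached proposal, none of which is at hand.** This is fair, and the missing units alone would not be a finding. But the protocol itself fixes Bland-Altman and agreement as the goal for an ELISA and a tissue-staining readout. A later document could rescue that only by calibrating both to one unit, or by departing from the sentence.

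3. **The illustration rests on assumed values, and nobody would be misled by limits of ±7816.** The values are assumed, and the size of any one entry should not be taken as a forecast. The dependence of the bias on units and the z-score identity are algebra and hold for any values. If r = 0.8 is read as a raw-scale correlation of lognormal data, the log factor is 1.71 and not 1.74, which changes nothing.

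4. **The consequence is limited.** This is a pilot, its hypothesis concerns amylin against neuropathy severity and nerve conduction, no rule for replacing the biopsy depends on this result, and the paired data will exist for a later correlation. All of that stands and keeps the point at modest weight.

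**Conclusion.** The concern holds. The protocol names a method for agreement and applies it to two readouts that it describes as different kinds of quantity, with no common scale. As written, the analysis cannot answer the question it is given: on the raw scale the bias is fixed by the unit (-20, 0 or +9970 in the illustration), on logs it still is (ratios 0.35, 1.04 and 346), and on z-scores the result only restates the correlation. The numbers rest on assumed means and SDs; the conclusion does not. It would fail only if both readouts were calibrated to one unit of the same quantity, and the protocol states no such calibration.

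The point should be fixed but is not critical. The correlations of each amylin measure with HbA1c and with the nerve conduction and sensory measures, and their power figure, are untouched.

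**What to change.** In the statistical analysis text under Study Design:

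1. Name one skin readout, with its unit, as the punch-biopsy measure.
2. Replace the Bland-Altman sentence with the RBC-skin correlation and its 95% confidence interval, and a regression of the skin readout on RBC amylin with 95% prediction intervals.
3. Describe the result as association or prediction, not agreement.
4. Keep Bland-Altman only for repeat readings of the same assay, if any are made.

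If the investigators do hold a calibration that puts both readouts in one unit, stating it would be an equally short repair. The cost is two or three sentences, with no new data, patients or procedures.

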Subject Recruitment Methods & Privacy: Describe plans for the identification and recruitment of subjects, including how the population will be identified, and how initial contact will be made with potential subjects by those having legitimate access to the subjects' identity and the subjects' information. Describe the setting in which an individual will be interacting with an investigator. If applicable, describe proposed outreach programs for recruiting women and minorities as participants in clinical research.

Please note: Based upon both legal and ethical concerns, the UK Medical Institutional Review Board (IRB) will not approve finder's fees for research studies.

Subjects will be identified from the patient population that has been previously diagnosed with DMII and who were referred to the Kentucky Neuroscience Institute Neuromuscular Laboratory for nerve conduction velocity studies (NCVs). The assessment for eligibility will be done by [name] who will ask potential participants if they would like to be part of a research study of patients with DMII who have been referred for NCVs. Patients deemed eligible for the study and interested in participating will be approached to undergo participation in this study by a member of the research staff qualified to consent patients for the study. Forty patients with previously diagnosed DMII and referred to the Kentucky Neurological Institute (KNI) Neuromuscular Laboratory for nerve

conduction velocity studies (NCVs) will be asked to participate in the study. Initially all patients with a diagnosis of DMII referred for NCVs will be asked to participate. After 20 participants have been recruited, an interim analysis of upper extremity NCV data will be reviewed by [name], who will then selectively recruit if necessary based on NCV data to insure a broad distribution of participants with range of NCVs from normal to severe. Information related to participants will be treated in strict confidence to the extent provided by law. Their identities will be coded with a unique number and will not be associated with any published results. The code number and identity will be securely kept in a locked office by the study coordinator.

[Back to Top](#)

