After signing an IRB-approved informed consent, all research subjects will have: • skin biopsy, 3 mm in diameter, taken from volar forearm using a standardized kit and vibratory sensation measured over the tip of the 2nd digit (index finger) quantified using a Rydel-Seiffer 128 Hz tuning fork). Skin biopsies will be collected and stored in formalin. • venipuncture for blood samples utilizing the UK Healthcare Clinical Laboratories (total volume = 30-60 ml). Blood samples will be collected for measure of RBC amylin (performed in [name] laboratory) and HbA1c (UK Healthcare Clinical Laboratories), as well as those measures not performed in the previous 6 months to include metabolic profile, complete blood count, vitamin B12, and thyroid stimulating hormone (UK Healthcare Clinical Laboratories). • pain/sensory testing will be conducted (as described below) to assess sensory responses. Pain/Sensory Testing Procedures: These assays have been safely implemented in our previous research studies (as indicated below) and are designed not to cause and tissue damage. a. Pressure Algometer Test: The pressure algometer test will be conducted using a computerized system (Medoc AlgoMed, U.S.A, Durham, N.C.). Pressure is applied at the rate of 40 kilopascals/sec with an algometer device will be applied to the thenar eminence (the area just below the thumb) on the palm side of the dominant hand. Two trials will be conducted, with at least 5 minutes separating each application. The main outcome measures for this test are 1) first detection of pressure sensation (sensory threshold) and 2) first detection of a painful sensation (pain threshold) (measured in kPa). We have safely used this procedure in previous studies (Protocols # 14-0769-F3R, 11-0816, 11-0980). b. Cold Pressor Test: Participants immerse their non-dominant forearm in a warm water (room temperature) bath for a total of 2 minutes. After the 2 minutes is complete, the participant is assisted in placing his/her forearm in a cold water bath (1.0°C ± 0.5°C) and is instructed to not touch the side or bottom of the water bath. Participants will report when they begin to feel pain (pain threshold) and will remove their arm from the water when they can no longer tolerate the pain (pain tolerance). Cold water immersion will last for a maximum of 5 min (a predetermined safety cut-off to prevent numbness or tissue damage). Pain threshold and tolerance (seconds of immersion) will be recorded manually. Our laboratory has previous experience safely using this procedure (IRB Protocols #14-0769-F3R, 06-0605, 11-0816, 11-0980). c. Cold Thermode Testing: A thermode will be applied to on the dorsal surface of the hand. The temperatures will start at approximately room temperature (approx. 35°C) and will steadily decrease (lowest possible temperature is 0° C). Volunteers will indicate when they begin to feel a cold sensation (sensory threshold) and the thermode will be removed when the participant reports the sensation of pain (pain threshold). If the participant does not report any pain, the thermode will be removed when the temperature reaches 0°C. Sensory and pain threshold are the main outcome measures and will be measured in temperature (e.g., the temperature at which they begin to feel

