
cold and the temperature at which they detect the pain). Our laboratory has previous experience safely using this procedure (IRB Protocols #14-0769-F3R). d. Heat Thermode Test: A thermode will be applied to the skin of the arm. Thermode temperature will begin at approximately room temperature (approx. 35°C) and will steadily increase (highest possible temperature is 53° C). Volunteers will indicate when they begin to feel a hot sensation (sensory threshold) and the thermode will be removed when the participant reports the detection of pain (pain threshold). If the participant does not report any pain during a given trial, the thermode will be removed when the maximum temperature is reached (53° C). Two applications will be conducted during trial. Sensory and pain thresholds are the main outcome measures and will be measured in temperature (e.g., the temperature at which they begin to feel a hot sensation and the temperature at which they begin to feel pain).

Attachments

Data Collection: List the data or attach a list of the data to be collected about or from each subject (e.g. interview script, survey tool, data collection form for existing data).

If the research includes survey or interview procedures, the questionnaire, interview questions or assessment scales should be included in the application (use attachment button below).

The data collection instrument(s) can be submitted with your application in draft form with the understanding that the final copy will be submitted to the IRB for approval prior to use (submit final version to the IRB for review as a modification request if initial IRB approval was issued while the data collection instrument was in draft form).

The following data will be collected: • Results from relevant laboratory analyses • Results from sensory examination • Results from peripheral nerve conduction velocities (NCVs) • Data from your medical record including duration of DMII diagnosis, current medications, height and weight • No other areas will be examined

Attachments

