Costs to Subjects: Describe any costs for care associated with research (including a breakdown of standard of care procedures versus research procedures), costs of test drugs or devices, and research procedure costs that are the subject's responsibility as a consequence of participating in the research. Describe any offer for reimbursement of costs by the sponsor for research related injury care.

There are no anticipated costs to the subject for care associated with this research.

Data and Safety Monitoring: The IRB requires review and approval of data and safety monitoring plans for greater than minimal risk research, clinical research, or NIH-funded/FDA-regulated clinical investigations.

If you are conducting greater than minimal risk research, clinical research, or your clinical investigation is NIH-funded/FDA-regulated, describe your Data and Safety Monitoring Plan (DSMP). [Click here for additional guidance on developing a Data and Safety Monitoring Plan.](#)

If this is a *non-sponsored investigator-initiated* protocol considered greater than minimal risk research, clinical research, or your clinical investigation is FDA-regulated, *and* if you are planning on using a Data and Safety Monitoring Board (DSMB) as part of your DSMP, [click here for additional guidance](#) for information to include with your IRB application. 

When participants appear for sensory testing at the UK Robert Straus Behavioral Science Laboratory, [name] on or about 1 week after venipuncture and skin biopsy, the sites will be examined by study personnel. If evidence of continued inflammation, infection or other abnormal appearance, [name] will examine site and treat as he opines medically appropriate. On or about 1 week after sensory testing, participants will be called and asked if they have any residual discomfort or other symptoms pertaining to the study. If a positive response, [name] will be informed and take action based on his best medical judgement.

[Back to Top](#)

Subject Complaints: Describe procedures (other than information provided in consent document) for handling subject complaints or requests for information about the research. The procedures should offer a safe, confidential, and reliable channel for current, prospective, or past research subjects (or their designated representative) permitting them to discuss problems, concerns and questions, or obtain information.

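### Is Pearson's correlation the wrong method for pain thresholds that can stop at a test limit?

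*Protocol*

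**What the plan says.** Under Study Design, the statistical paragraph correlates each amylin measure with HbA1c and with the NCV and sensory examination measures. It adds "Correlations will be based on Pearson"'s coefficient and claims 80% power for a correlation of 0.414 with 40 patients at the 0.05 level.

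Research Procedures sets three test limits:

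- Cold pressor: "Cold water immersion will last for a maximum of 5 min". Tolerance is recorded as seconds of immersion.
- Cold thermode: "If the participant does not report any pain, the thermode will be removed when the temperature reaches" 0°C. The pain threshold is "the temperature at which they detect the pain".
- Heat thermode: if no pain is reported, "the thermode will be removed when the maximum temperature is reached" (53°C).

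The protocol gives no scoring rule for a participant who reaches a limit and no expected share of such participants. It does not say that anyone will be excluded.

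Whether the pain tests belong to the correlated sensory measures is not stated outright. Data Collection lists "Results from sensory examination" and no other entry that could hold them, and Data and Safety Monitoring writes "When participants appear for sensory testing at the UK Robert Straus Behavioral Science Laboratory" of the pain visit. On the other side, the Aim under Objectives speaks of a clinical sensory examination. Study Design describes tuning-fork vibration testing at the biopsy step and labels the pain tests separately.

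**The concern.** Pearson's coefficient needs a number for every participant. A thermode pain threshold defined by the detection of pain gives none for someone who feels no pain before the limit, and the cold pressor cut-off gives only a lower bound. Recruitment may be steered towards a "broad distribution of participants with range of NCVs from normal to severe", so participants who feel little may well be enrolled, and they could be the ones most informative about severity.

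If they were dropped, the analysis would lose both numbers and range. In a pilot of 40 patients, meant to supply preliminary data for a larger trial, a real correlation could be missed or understated. A rank method that keeps them at a tied worst rank appears to avoid this. Set beside Pearson with those participants dropped, it looks far better: 71, 71 and 69% power against 59, 46 and 36%.

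**Working it through.** **Inputs.** From the protocol: n = 40, r = 0.414, alpha = 0.05 (taken as two-sided), power 80%. Assumed, because the protocol gives no figure: 10, 20 or 30% of participants at a limit, and bivariate normal data.

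**The plan's own figure.** With the two-sided noncentral t test on 38 degrees of freedom:

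- noncentrality = √40 × 0.414 / √(1 − 0.414²) = 6.325 × 0.414 / 0.910 = 2.88
- power = 0.8004

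The stated 80% reproduces. This calculation treats one variable as fixed. When both vary, simulated power with complete data is about 77% for Pearson and 72% for Spearman. Those two values are the baseline below.

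**A like-for-like comparison.** Two things can vary: the coefficient, and what is done with participants at the limit. To see which one matters, change one at a time. Simulated power at true r = 0.414, 20,000 studies per setting:

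| Handling of limit cases | Coefficient | 10% | 20% | 30% |
|---|---|---|---|---|
| Limit value entered | Pearson | 76% | 74% | 71% |
| Limit value entered (tied rank) | Spearman | 71% | 71% | 69% |
| Left out | Pearson | 59% | 46% | 36% |
| Left out | Spearman | 53% | 41% | 31% |

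Repeat runs agree to within about two points.

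*Effect of leaving cases out, same coefficient:*

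- Pearson: 76 − 59 = 17, 74 − 46 = 28, 71 − 36 = 35 points lost.
- Spearman: 71 − 53 = 18, 71 − 41 = 30, 69 − 31 = 38 points lost.

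*Effect of changing Pearson to Spearman, same handling:*

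- Limit value entered: 76 − 71 = 5, 74 − 71 = 3, 71 − 69 = 2 points lost.
- Left out: 59 − 53 = 6, 46 − 41 = 5, 36 − 31 = 5 points lost.

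The apparent advantage of ranks compares Pearson with cases dropped to Spearman with cases kept, so it changes both things at once. At 10% that gap is 71 − 59 = 12 points: 17 gained by keeping the participants, less 5 given up by ranking. At 20% it is 28 − 3 = 25, and at 30% it is 35 − 2 = 33.

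**Cost of the simple entry.** With 0°C or 53°C entered (and 5 × 60 = 300 s for the cold pressor), Pearson's mean estimate is 0.41, 0.40 and 0.38 at 10, 20 and 30%, against 0.41 with complete data. At 30%, power falls by 77 − 71 = 6 points. Type I error stays near 5% in every setting.

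**Is a value really absent?** For cold pressor tolerance it is not: seconds of immersion has a recorded value at the cut-off. The point applies to pain thresholds only. For the thermodes the temperature at which the test ends is known.

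**The case for a change.** The best case for the concern is that Pearson is fixed here for every measure, while the pain threshold as defined can yield no number. That is a choice made in the protocol, not a silence. It can be added that dropping even one or two of 40 participants matters: with 5% dropped, Pearson's power is 67%, below the 72% of Spearman with everyone kept. Ranks also need no numerical value for a limit case, so they protect against an arbitrary extreme code. With such cases coded 10 SD beyond the mean, Pearson's power is only 54, 57 and 60%.

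Some of this stands. A literal reading of the thermode definition leaves a participant without pain unscored, and excluding such participants would be harmful. Ranks would indeed help against extreme coding. But nothing in the protocol plans exclusion or extreme coding, and the natural entry is the temperature or time at which the test ended. Spearman gives no protection against exclusion either, so a rule to keep these participants would be needed whichever coefficient is used. With that rule in place, Pearson does slightly better.

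The same argument has been extended to unrecordable NCVs. The protocol mentions none, so that part rests on an assumption from outside the document.

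**Conclusion.** The concern does not hold. The stated power reproduces, and naming Pearson is not what would cause a loss. With the limit value entered, Pearson is 2 to 5 points ahead of Spearman; with cases left out it is 5 or 6 points ahead. The 17 to 35 points at risk for Pearson depend on excluding participants, which the protocol does not propose.

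Moving NCV and the pain outcomes to a rank method would give up about 5 points with complete normal data (77% to 72%). It would also raise the correlation detectable with 80% power from about 0.43 to 0.45 or 0.46. That is a preference on which statisticians differ, not the correction of an error.

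What remains is an unwritten rule for scoring participants at a test limit. A protocol commonly leaves that to the statistical analysis plan, which was not available here. These figures assume normal data, a true correlation of 0.414 and 10 to 30% at a limit. The conclusion is the same whether or not the pain tests count among the sensory examination measures.
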